10.4.3 Safety analyses

The reporting of safety data is descriptive, and will include all subjects in the Safety population. The variables for safety endpoints are AEs. AEs will be summarized based on their frequency and their severity. All AEs will be coded using Medical Dictionary for Regulatory Activities (MedDRA) and summarized by treatment group. Data will be summarized using preferred term and primary system organ class.

If a subject experiences multiple events that map to a single preferred term, the greatest severity and strongest Investigator assessment of relation to study product will be assigned to the preferred term for the appropriate summaries. Should an event have a missing severity or relationship, it will be classified as having the highest severity and/or strongest relationship to study product.

Summaries of treatment-emergent AEs will include any AEs reported beginning with the first dose of study product on Day 0. The occurrence of treatment-emergent adverse events will be summarized by treatment group using preferred terms, system organ classifications, and severity. Separate summaries of treatment-emergent serious adverse events, treatment-emergent adverse events related to study drug, and events leading to the discontinuation of study drug will be generated. All adverse events reported will be listed for individual subjects showing both verbatim and preferred terms.

Concomitant medications will be coded using the World Health Organization (WHO) drug dictionary. These data will be summarized for all subjects. Previous and concomitant medications will be presented in a data listing.

10.5 Sample Size

Sample size is 52. The requisite sample size for the *t*-test of the means of independent samples, assuming a Cohen's *d* of .40, alpha .05 two-tailed, and a power of .80, was smaller at 44. Thus, the larger requisite sample size for the *z*-test will also suffice for the *t*-test and will provide a cushion for the application of the Holm correction for Type I error. The sample size of 52 should be increased to account for a 10% expected dropout rate, resulting in a total sample size, rounded to an even number, of 58 (26 per group).

Expected difference:

40% difference between treatment groups, based on results of LiceFreee Spray (1% Sodium Chloride) compared to Permethrin; the results showed significantly higher pediculicidal activity for Sodium Chloride spray (85%) as compared to Permethrin (45%) at Day 15 ($p < 0.05$)¹.

A pilot study using Vamousse Spray 'n' Go as a once only treatment, showed high early lice kill (88% lice free at day 0 after treatment) but low efficacy at day 14 (12% lice free). It is anticipated that repeat dosing after 7 days, if live lice are present, will boost day 14 efficacy to levels similar to those at day 0.

Assumptions:

80% power, 0.05 alpha
Allocation ratio 1:1

Methods:

Calculations performed in Stata/IC 16.1
Binary data (lice free – Y/N) – proportions
Independent samples
Chi Squared, two-sided test

Sample:

Estimated sample sizes for a two-sample proportions test
Pearson's chi-squared test
 $H_0: p_2 = p_1$ versus $H_a: p_2 \neq p_1$
Study parameters:

```
alpha = 0.0500
power = 0.8000
delta = 0.4000 (difference)
p1 = 0.4500
p2 = 0.8500
```

Estimated sample sizes:

$N = 52$
 N per group = 26
Allowance for drop out: 10% per group, 3
Total sample: 29 per group (58)

References:

¹ Serrano, L. et al. Evaluation of the Efficacy and Safety of 1% Sodium Chloride (LiceFreee Spray) against 1% Permethrin Crème Rinse on Head Lice Infested Individuals. *Pharmacology & Pharmacy*, 2013, 4, 266-273.

11 Source documents and access to source data/documents

The Investigator/institution will permit study-related monitoring, audits/inspections, IRB/IEC review and regulatory inspection providing direct access to source documents, including all medical records or pertinent data relevant to the audit/inspection. Source documents will represent a record of the raw data. Source document templates may be provided by either the clinical site, Sponsor representative, or the Sponsor. If provided by the clinical site, the source document template must be provided to the Sponsor prior to subject recruitment. The source documents will become part of the subject's permanent medical record maintained by the clinical site. If computerized systems are used to create, modify, maintain, archive, retrieve or transmit source data, they must comply with the applicable regulatory regulations and/or guidance (ex. 21 CFR Part 11 and 312).

12 Ethics/subject protection

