10.3 Statistical hypotheses

Primary Efficacy Endpoint:

Primary Outcome:

The proportion of subjects who are lice free (defined as no live lice, adults or nymphs) at day 14 will be greater in the treatment group than in the control group.

Secondary Outcome:

The mean change between day 14 and baseline in the counts of live lice (i.e., total of live adult lice and nymphs) will be greater in the treatment group than in the control group.

Secondary Efficacy Endpoint:

Primary Outcome:

The proportion of subjects who are lice free (defined as no live lice, adults or nymphs) at day 7 will be greater in the treatment group than in the control group

Secondary Outcome:

The mean change between day 7 and baseline in the counts of live lice (i.e., total of live adult lice and nymphs) will be greater in the treatment group than in the control group.

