10.4.2 Assessment of primary and secondary endpoints

Primary Outcome:

To test the hypotheses for this outcome for each of the two endpoints, the counts of subjects in the treatment and control groups who were lice free at each endpoint will be converted into proportions of the respective group. These proportions along with the group sample sizes will be used to compute the necessary Z statistics for independent proportions.

Secondary Outcome:

To test the hypotheses for this outcome for each of the two endpoints, the difference between the day 14 and baseline counts of live lice (i.e., total of live adult lice and nymphs) will be computed for each participant. The mean difference in counts for the treatment and control groups will be tested using the t-test for independent means.

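### Section 10.5 gives 44 subjects for the lice-count t-test at d = 0.40; its own inputs require 200, so 52 subjects give about 29% power, not 80%

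*Combined protocol and SAP*

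**What the plan says.** Section 10.5 (Sample Size) opens with the requirement for the comparison of lice-free proportions: "Sample size is 52". It then gives the requirement for the t-test of independent means at a Cohen's d "of .40, alpha .05 two-tailed, and a power of .80, was smaller at 44". Because 44 is below 52, it concludes that the larger figure covers the t-test too, and that it "will provide a cushion for the application of the Holm correction for Type I error". That sentence is the plan's only mention of Holm.

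The t-test is a planned analysis. Section 10.4.2 says of the change in live-lice counts: "The mean difference in counts for the treatment and control groups will be tested using the t-test for independent means". Section 10.3 states directional count hypotheses at day 14 and also for "The mean change between day 7 and baseline in the counts of live lice". Section 4.2.3 lists the day-14 change in counts as a secondary endpoint.

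**The concern.** A standardised difference of 0.40 lies between the conventional small and medium effects. Detecting it with 80% power in a two-group comparison takes roughly 100 subjects per group, so a total of 44 is too small by a factor of more than four. Two further statements in 10.5 rest on the 44: that 52 is enough for the t-test, and that there is spare capacity for a multiplicity correction.

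At stake is how the secondary count result will be read. Anyone relying on 10.5 would believe that this comparison has at least 80% power at the assumed effect, and could take a non-significant result as informative evidence against a difference. The primary analysis and the number enrolled are not at stake.

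**Working it through.** **Inputs, all from section 10.5 unless noted**
- Test: t-test of two independent groups on each participant's change in count (10.4.2)
- Effect: d = 0.40
- Error rate: "alpha .05 two-tailed"
- Power: 0.80 ("and a power of .80")
- Allocation: "Allocation ratio 1:1"
- Evaluable subjects: 52 (26 per group); enrolled: 58 (29 per group)

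**Step 1. Try to reproduce 44.** The normal approximation is n per group = 2(z₀.₉₇₅ + z₀.₈₀)² / d² = 2(1.960 + 0.842)² / 0.16 = 98.1, so 99. The exact noncentral-t solution is 99.08, so 100 per group and 200 in total. The stated 44 is not reproduced.

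**Step 2. Try other readings of 44.**

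| Reading | Result |
|---|---|
| 44 is per group (88 in total) | 45.8% power |
| One-sided alpha 0.05 | 77.97, so 78 per group (156 in total) |
| Paired or one-sample, two-sided | 51.01, so 52 |
| Paired or one-sample, one-sided | 40.03, so 41 |
| 0.40 is Cohen's f, two groups | 51.05, about 52 in total |

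None gives 44 for 80% power.

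**Step 3. Power actually available at d = 0.40.** Power is the probability that a noncentral t with 2n − 2 degrees of freedom and noncentrality d√(n/2) exceeds the two-sided critical value in absolute size.
- n = 26: noncentrality 0.40 × √13 = 1.442, critical value 2.009 on 50 df, power 29.3%
- n = 29: noncentrality 0.40 × √14.5 = 1.523, critical value 2.003 on 56 df, power 32.2%

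Solving the same expression for d at 80% power gives 0.79 with 26 per group and 0.75 with 29. A total of 44 (22 per group) would need d = 0.86.

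**Step 4. The cushion for Holm.** The shortfall before any correction is 200 − 52 = 148 subjects, so there is no spare capacity. The plan does not define the Holm family. If the count test had to pass at the first Holm step, the figures with 26 per group would be:

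| Family | First-step alpha | Power at d = 0.40 | d for 80% power |
|---|---|---|---|
| Two tests | 0.025 | 20.2% | 0.88 |
| Four tests (all hypotheses in 10.3) | 0.0125 | 13.6% | 0.96 |

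These are lower bounds on power under Holm, because later steps use larger alphas once an earlier hypothesis is rejected.

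**Step 5. Check the primary calculation.** For 45% versus 85%, two-sided alpha 0.05 and 80% power, the two-proportion formula gives 21.1, so 22 per group (44 in total) without continuity correction. With the correction it gives 25.9, so 26 per group (52 in total). The plan's 52 therefore reproduces with the correction, although the printed output names only Pearson's chi-squared test. The uncorrected total equals the 44 attributed to the t-test. It may have been carried over from there, but the document does not say so and nothing here depends on it.

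**The case against.** The arithmetic is not in dispute; the objections concern its weight and the remedy.

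- **The effect size has no support.** The documents give no standard deviation or source for d = 0.40, so 29% is conditional on an unexplained figure. It also assumes independent subjects, while infested household members go to the same group as the index case (4.1, 7.3.1). Both points are correct. Neither defends the 44, because the error is that the plan's own inputs do not give its own output. If a larger effect is expected, 10.5 should state it.
- **First-step Holm power overstates the loss.** This stands. If the family is the primary comparison plus the count test, with 45% versus 85%, d = 0.40, 26 per group and the two tests treated as independent, simulation gives about 28% power for the count test under Holm, against 29% unadjusted. The 20% and 14% figures should be read only as lower bounds. Power is still no higher after Holm than before it, so the cushion remains unsupported.
- **The consequence is limited.** No sample size, endpoint, method or primary conclusion uses the 44, and section 10 promises confidence intervals for the primary and secondary efficacy endpoints, which would show the imprecision. This holds the point to a correction of moderate weight. It does not make a false power statement acceptable.

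**Conclusion.** The concern holds. On the inputs stated in 10.5 the t-test needs 200 subjects, not 44, and both conclusions drawn from the 44 are wrong for the count outcome. At d = 0.40, two-sided alpha 0.05 and independent subjects, power is about 29% with 52 evaluable and 32% with 58, so a true effect of the assumed size would be missed about 70% of the time. The detectable effect at 80% power is about 0.79 with 52, roughly twice the effect assumed. Whether 0.40 is realistic cannot be judged from the documents. The lice-free comparison and the targets of 52 and 58 stand. This should be corrected, but it does not threaten the primary result.

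**What to change.** In section 10.5, delete the figure of 44 and the statements that the z-test sample size covers the t-test and leaves room for Holm. Replace them with text such as:

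> The sample size is set by the primary lice-free comparison. For the secondary lice-count t-test, 26 evaluable subjects per group give about 29% power at d = 0.40, and 80% power only for d of about 0.79 or more (two-sided alpha 0.05, before Holm adjustment; power is lower after it). The Holm correction will be applied. A non-significant count result will not be read as evidence of no difference.

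The explicit Holm sentence is needed because the passage being replaced is the only place where the plan commits to it. If the sponsor can justify a different d, that value, its source and the matching power should replace 0.40 and 29%.

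The cost is two or three sentences and a less favourable power statement for a secondary outcome. Enrolment, visits, data collection, endpoints and analysis methods are unchanged.

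### Holm is named only in the sample-size section, its family is undefined, and the claimed cushion does not cover all four hypotheses at alpha 0.05

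*Combined protocol and SAP*

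**What the plan says.** Section 10.5 sets the primary comparison at "80% power, 0.05 alpha", by "Chi Squared, two-sided test", with 45% against 85% lice-free and "Allocation ratio 1:1". The result is 26 per group, 52 in all. The dropout line, "Allowance for drop out: 10% per group, 3", brings enrolment to 29 per group, 58 in all. (The opening paragraph of 10.5 puts 26 per group beside the total of 58; the output at the end of the section shows that 29 is meant.)

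For the count outcome, 10.5 gives a t-test sample size of 44, "assuming a Cohen's *d* of .40", two-sided 0.05 and 80% power. It concludes that the larger z-test figure covers the t-test too and "will provide a cushion for the application of the Holm correction for Type I error". That is the only mention of Holm.

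Section 10.3 lists four hypotheses: lice-free proportion and change in live-lice count, each at Day 14 and Day 7. The fourth begins "The mean change between day 7 and baseline in the counts of live lice". Sections 10.1 and 10.4.2 describe Z tests and t-tests with no adjusted alpha, family or testing order.

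**The concern.** Holm orders the p-values and compares the smallest with alpha/k, the next with alpha/(k - 1), and so on. If the Day 14 lice-free test shares a family of k, it may have to clear 0.05/k, yet its sample size was set at 0.05.

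Two things are at stake. The first is power: the primary may pay for weaker secondary tests. The second is interpretation. Take a primary p-value of 0.03. Tested alone it is significant. In a family of two or four it is not, unless enough of the other tests reject first. With the family unstated, that choice could be made after the data are seen.

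**Working it through.** **Inputs.** From 10.5: p1 = 0.45, p2 = 0.85, two-sided alpha 0.05, power 0.80, 26 per group evaluable, 29 enrolled, d = 0.40. From 10.3: four hypotheses. From 5.4: 52 expected completers. Assumed, because the documents do not give them: correlation 0.5 between outcomes and a Day 7 test-arm lice-free rate of 50 to 85%.

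**Step 1. Reproduce 52.** The mean proportion is 0.65, so 2(0.65)(0.35) = 0.455, and 0.45(0.55) + 0.85(0.15) = 0.375.

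Plain Pearson: n = (1.960√0.455 + 0.8416√0.375)² / 0.40² = 21.1, so 22 per group, 44 in total.

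With continuity correction: n' = (n/4)(1 + √(1 + 4/(0.40n)))² = 25.9, so 26 per group, 52 in total. Then 52/0.90 = 57.8, so 58.

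The stated 52 therefore reproduces at alpha 0.05 only with the continuity correction. Plain Pearson at alpha 0.025 gives 25.7, also 26 per group, but the stated alpha is 0.05.

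**Step 2. Primary power at each possible Holm threshold.** Normal approximation: Φ[(0.40 - z√(0.455/n)) / √(0.375/n)]. At n = 26 and alpha 0.0125 this is Φ[(0.40 - 2.498 × 0.1323)/0.1201] = Φ(0.58) = 71.9%. The exact columns sum binomial probabilities over all outcomes of the pooled Z test. The corrected column replaces 0.40 by 0.40 - 1/n.

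| Two-sided alpha | 26/group, normal | 26/group, exact Z | 26/group, continuity-corrected | 29/group, exact Z |
|---|---|---|---|---|
| 0.05 (alone) | 87.9% | 89.4% | 80.3% | 91.0% |
| 0.025 (k = 2) | 80.6% | 83.2% | 70.6% | 86.0% |
| 0.0167 (k = 3) | 75.6% | 77.6% | 64.6% | 82.7% |
| 0.0125 (k = 4) | 71.9% | 75.4% | 60.2% | 79.3% |

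Section 10.1 plans an uncorrected Z test, so the exact Z columns are the relevant ones. Its fallback for counts below 10, taken as Fisher's exact test, changes them little at 26 per group: 89.3%, 83.0% and 75.1% at 0.05, 0.025 and 0.0125.

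**Step 3. Full Holm procedure.** The table gives the strictest threshold for each k. The primary's power under Holm lies between that row and the 0.05 row. Simulating all four tests at d = 0.40 and correlation 0.5 gives about 76 to 78% for the primary at 26 per group and about 79 to 82% at 29. A normal-approximation simulation over correlations from 0 to 0.8 gives 72 to 76% at 26 per group.

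**Step 4. Why the step-down helps little.** The threshold for the primary relaxes only when another test rejects first. For the t-test at 26 per group, the noncentrality is 0.40√(26/2) = 1.44. Its power is about 29% at 0.05 and 14% at 0.0125.

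**Step 5. Check the 44.** n per group ≈ 2(1.960 + 0.8416)²/0.40² = 98; the t distribution gives just over 99, so 100 per group, about 200 in total. A total of 44 corresponds to d of about 0.86. Even read as 44 per group, it is less than half of what d = 0.40 needs.

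**The case against.** A reader might infer that the plan places the primary in a four-test Holm family and that the trial therefore misses 80% power outright. The documents do not support that. They never define the family, and the analysis sections give unadjusted tests. If the primary is tested alone at 0.05, there is no loss.

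A two-test reading is also open, because the Holm sentence sets the z-test beside the t-test. On that reading exact power is at least 83%, and 26 per group is what plain Pearson requires at 0.025. The cushion would then be real for the test that 10.1 plans.

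Even with four tests, the gap depends on assumptions. If the count effects match the 44 rather than the stated 0.40 (d about 0.86) and the Day 7 effect is strong, primary power reaches about 84%. Section 10.2 also keeps early discontinuers in the mITT by carrying the last observation forward, so the analysed number may be nearer 29 than 26. However, 10.2 names the per-protocol set as primary for the between-group comparison, so 26 remains a fair planning figure.

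Finally, Holm with the primary inside is a valid way to control familywise error. The choice between it and a fixed sequence is one of design.

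All of this stands, and it makes the power loss conditional. It does not answer the undefined family or the wrong 44. The contrary inference, that the primary is inside, also has some basis: the cushion is claimed for the z-test sample size, and a primary tested alone at 0.05 would need none.

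**Conclusion.** The point holds as a gap in specification with a conditional cost in power. What is firm: the sample size was set at unadjusted 0.05, Holm is named once with no family, no rule protects the primary, and the t-test figure of 44 does not follow from its stated inputs.

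What is conditional: with all four hypotheses of 10.3 in one Holm family, 26 completers per group and the effect sizes in 10.5, primary power is about 76 to 78% against the stated 80%. This rests on the assumed correlation of 0.5 and the assumed range of Day 7 rates. At 29 per group the result is roughly on target, and with two tests the target is met. The t-test has about 29% power at 26 per group whatever family is chosen, even before any correction.

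**What to change.** 1. In 10.1, state that Day 14 lice-free is tested first and alone at two-sided 0.05. Only if it is significant are the listed secondary hypotheses tested, with Holm among themselves at 0.05. Carry the same rule into 10.4.2.
2. Name those secondary hypotheses. The synopsis gives lice-free at Day 2, 10.3 gives Day 7, and 4.2.3 has a longer list. These must be reconciled before the sequence can be run.
3. In 10.5, delete the cushion sentence and the claim that 52 suffices for the t-test. State the t-test's actual power (about 29% at 26 per group for d = 0.40, unadjusted), or justify a different d. Deleting the cushion wording alone would leave the wrong 44 in place.

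Under the four-test reading this recovers about 11 to 13 points of primary power at 26 per group (89.4% less 76 to 78%) and still controls familywise error. It costs wording and no subjects. The downside is that no confirmatory secondary claim is possible if the primary fails.

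The alternative is to keep all four hypotheses in one family and size the primary at 0.0125. That needs 31 per group by the Z test (62 evaluable; 62/0.90 = 69 enrolled, or 70 for equal arms), or 36 per group with continuity correction (72 evaluable; 72/0.90 = 80 enrolled).

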12.1 Ethical standard

The study will be conducted according to the protocol, GCP, as outlined in the ICH Guidelines and Code of Federal Regulations. Written informed consent for the study must be obtained from all subjects before protocol specific procedures are performed. Subjects must be informed of their right to withdraw from the study at any time and for any reason.

12.2 IRB

It is the responsibility of the Investigator to have prospective approval of the study protocol, protocol amendments, informed consent forms, and other relevant documents, (e.g., recruitment advertisements, subject's diaries, if applicable) from the IRB/IEC. All correspondence with the IRB/IEC will be retained in the Investigator File. Copies of IRB/IEC approvals should be forwarded to the Sponsor or its designee.

The only circumstance in which an amendment may be initiated prior to IRB/IEC approval is where the change is necessary to eliminate apparent immediate hazards to the subjects. In case of such an event, the Investigator must notify the IRB/IEC and the Sponsor in writing immediately after the implementation.

12.3 Informed Consent Process

12.3.1 Other information documents provided to participants

In addition to IRB/IEC approval, all other required approvals (e.g. approval from local Research and Development Board or Scientific Committee) required by the individual site for participating in this study will be obtained by the Investigator prior to recruitment of subjects into the study and shipment of the investigational product(s). It is the responsibility of the Investigator to notify the Sponsor of the requirement of such approvals prior to participating in the study.

12.3.2 Consent procedures and documentation

It is the responsibility of the Investigator to give each subject (or the subject's acceptable representative), prior to inclusion in the trial, full and adequate verbal and written information regarding the objective and procedures of the trial and the possible risks involved. The subjects must be informed about their right to withdraw from the trial at any time.

Furthermore, it is the responsibility of the Investigator, or a person designated by the Investigator, to obtain signed informed consent forms from each subject or the subject's legally acceptable representative prior to inclusion in the trial. The Investigator will retain the original of each subject's signed consent form.

The informed consent form will be in compliance with ICH GCP, local regulatory, and legal requirements. The informed consent form used in this study, and any changes made during the course of the study, must be prospectively approved by both the IRB/IEC and the Sponsor before use, and shared with the subject and/or their representative for continued inclusion in the study

